3.6.2 Change of Centres

Due to the ongoing pandemic participants may be required to move hospitals. No IMP will move with the participants and hence dosing will stop. Prophylactic antibiotic use will continue where appropriate.

If participants are moved to a hospital within the study then safety (conmeds, AEs, labs and temperature) and key efficacy data (primary oxygenation endpoint, ordinal scale, respiration data and mortality) will be prioritised.

If participants are moved to a hospital outside the conduct of the study then only key safety data (conmeds, AEs, SAEs) will be collected.

Centre changes will be captured and reported as well as day of transfer. Data collected for participants after transfer to another hospital may not be included in any formal analyses, but will be listed.

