4.2 Handling of dropouts or missing data

The SOE indicates some endpoints are listed as only being collected on the specified days where comparisons between treatments are required, but all clinical and laboratory endpoints will be collected as frequently as possible, preferably daily, whilst in hospital. The primary assessment period is for 28 days post randomization, but some endpoints cannot be collected once a participant has been discharged from hospital e.g. vital signs (including the primary endpoints) and laboratory endpoints.

See Section 5.1 for definitions for Completed Treatment and Completed Study and their complements.

Missing values from participants take 4 forms:

- Missing due to death (no longer 'at risk' of recovery)
- Missing due to hospital discharge prior to end of primary assessment period (on any day up to D28)
- Missing values from the ideal of having daily collection of laboratory and clinical endpoints whilst participants are in hospital
- Missing values due to premature withdrawal from study

How missing data are to be handled is described in the analysis sections for each endpoint.

Participants who discontinue *study treatment* for reasons other than death or hospital discharge (for example, withdraw consent or adverse event, may still continue on study and will have measurements taken, so data from timepoints following discontinuation from *study treatment* will not be missing. These participants/data may be considered differently as part of a sensitivity analysis as they did not receive treatment per protocol.

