8.2 Statistical analysis of the secondary efficacy endpoint(s)

There are several secondary endpoints that cover each of the secondary objectives and a list is provided in the table listing the secondary endpoints in Section 2.2.1.2. Some of these endpoints are different derivations from the same collected data. In addition, some of the endpoints collected for one objective, may be the inputs to derivations for endpoints for the same objective or for another objective.

Data types for the secondary efficacy endpoints fall into the following main categories: continuous (for example, change from baseline (including the various ordinal categorical endpoints), number of days with 'condition'), ordinal categorical, binary ('responder' Y/N), time to event or duration of event.

Table 8.1 describes the analyses of each secondary endpoint listed in Section 2.2.1.2 and identifies which efficacy objective (2-6) the endpoint is addressing. Brief details of any derivations and analysis methods used are provided. Further details are included in the mock TFL shell document. In the event the data for some of these endpoints indicate that analysis through fitting models is not appropriate, for example too few events for a formal analysis on response or mortality rates, or time to event analyses, the analyses will not be carried out and only listings, figures and summaries provided.

Some patients may withdraw from the study or be transferred to another hospital prior to discharge through medical improvement. If data have been collected from another hospital post discharge from the first hospital, these data will be listed. This will be for variables or derived variables which would have included data from these patients. For example, duration of stay in hospital. However, for variables only including data up to a relative day prior to discharge/transfer from the first hospital, these patients will be included in the analysis/summary

for that period but set as missing for the other periods. Residual plots will be reviewed to determine any influence these participants may have had on the results.

Table 8.1

Endpoint	Derivation	Analysis

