
patient remained in hospital, the patient will be classified as a responder, even though the 2-point change had not been ‘sustained’.
	
date). If Time to Response >15 and censor=1 for analysis up to D15, Time to Response=15. If Time to Response >28 and censor=1 for analysis up to D28, Time to Response=28. For patients who have died Time to Response is set to D15 or D28 respectively and censored at this time. Note: Treatment will be merged into the TTE dataset. In addition to other variables that may be used as covariates in final analysis.
 
(one line per participant dataset)
	

Objective 2 Percentage of participants reporting at least a 2-point improvement sustained to D28 or discharge
	
Use D28 response indicator variable defined above
	
PROC FREQ/PROC LOGISTIC(if covariates are added) Model: Response=ACTARM +covariates (if added) Output percentage response on each treatment. Odds ratio and 95% confidence interval

Objective 2 AUEC/Time using the 6-point score recorded daily – up to D15, D28 and all data recorded
	
For each participant calculate the area under the curve and divide by 15 for up to D15 and by 28 for up to D28 (higher average score per day the better the response). Use last value brought forward for any missing values until next data entry. For discharge, carry forward score=6 for each day post discharge day. For death, carry forward score=1 for each day post death day.
	
Analyse AUEC/Time using analysis of variance with ACTARM as a two-level factor and baseline score as a covariate

Endpoint	Derivation	Analysis

Objective 2 Percentage of participants who record at least 2-point improvement from baseline or discharge (response) between D1-D6, D7-D15 and D16-D28
	
Responder classified as above. Create indicator variable (3 levels) if the relative day of START of response is between D1 and D6, between D7 and D15 or between D16 and D28. Each responder participant can only be within one of these categories. Participants who have a missing value are classified as non-responders
	
Frequency table and percentage responders in each of the categories defined by the indicator variable, by treatment. Exact 95% confidence intervals for each percentage

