
Objective 2
 
Number of days with hypoxia (defined as SpO₂ <93% breathing room air or the dependence on supplemental oxygen after randomisation to Day 28 (or discharge, whichever comes earlier)
	
Use SpO₂ (%) and Suppl O₂ (Y/N) from Vital parameters to derive indicator variable which flags each day where this condition holds.
 
Derive variable per participant that gives total number of days with condition
	
Summary statistics of variable with Total number of days: n, mean, SD, median, minimum, maximum
 
By treatment arm

Endpoint	Derivation	Analysis

Objective 3 Duration of ventilator free days after randomisation to Day 28 (or discharge, whichever comes earlier)
	
Use data from Vital parameters (include all days, where NIV, IV and ECMO='N')
	
Summary statistics of variable with Total number of days: n, mean, SD, median, minimum, maximum By treatment arm

Objective 3 Duration of invasive mechanical (including ECMO) and non-invasive mechanical ventilation in ventilated participants
	
Complement of above (exclude participants who are not ventilated i.e. do not include these with a duration of 0)
	
Summary statistics of variable with Total number of days: n, mean, SD, median, minimum, maximum By treatment arm

Objective 3 Time since randomization until first use of high-flow oxygen devices or non-invasive mechanical ventilation or invasive mechanical ventilation or ECMO in non-ventilated participants (i.e. excluding participants who are ventilated within 24h prior to or after randomization) during 28-day assessment period
	
Use Vital Parameter CRF and the method of supplementary oxygen variable. Use the date from this CRF to identify when first use occurred. Indicator variable to identify sub-group to be included. Censor if never used any of these ventilation methods at Day 28
	
Kaplan-Meier analysis using PROC LIFETEST. Strata ACTARM. Request Survival plot adjusting axis and heading titles to reflect progression and not response Output statistics: Appropriate statistics from analysis as indicated in mock shell

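### The time-to-first-ventilatory-support row in SAP Table 8.1 has one censoring rule, Day 28 for all never-users, and no rule for death, withdrawal or transfer

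*SAP*

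**What the plan says.** The endpoint is in SAP section 8.2, Table 8.1, under Objective 3, and is restricted to participants not ventilated within 24 hours either side of randomization.

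- **Event date:** taken from the Vital Parameter CRF: "Use the date from this CRF to identify when first use occurred".
- **Censoring:** one instruction, "Censor if never used any of these ventilation methods at Day 28".
- **Method:** "Kaplan-Meier analysis using PROC LIFETEST. Strata ACTARM", with a survival plot relabelled to show progression.

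The row does not mention death, withdrawal, transfer or live discharge.

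Three other places in the SAP bear on this:

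- Section 4.2 lists death and premature withdrawal as separate sources of missing values and then defers: "How missing data are to be handled is described in the analysis sections for each endpoint".
- The text introducing Table 8.1 deals with patients who withdraw or change hospital. For variables that use data only up to a day before they leave, they are included "for that period but set as missing for the other periods". No censoring date is given, and death is not covered.
- Section 3.6.2 says "If participants are moved to a hospital outside the conduct of the study then only key safety data (conmeds, AEs, SAEs) will be collected", and also "Data collected for participants after transfer to another hospital may not be included in any formal analyses, but will be listed".

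Neighbouring rows are more specific. Time to ARDS stops non-progressors at the earlier of discharge and 28 days. Time to a 2-point improvement has rules for withdrawal, for discharge without improvement and for death: "For patients who have died Time to Response is set to D15 or D28 respectively and censored at this time".

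**The concern.** The event is an adverse one. On a survival plot of an adverse event, remaining event-free to Day 28 is the best result a participant can have. The literal rule gives that result to someone who dies on Day 5 without support, and to someone last seen on Day 3. In the 2-point-improvement row, holding deaths to the end of follow-up is unfavourable to the patient because the event is a good one. Here the same treatment looks favourable.

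Losses raise a separate problem. A person moved to a non-study hospital has no respiratory data collected there, so a first use of support would not be seen, yet the row keeps that person at risk and event-free.

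Progression to mechanical ventilation and/or ARDS is a secondary objective (Protocol 3.2, SAP 2.1.2). If unsupported deaths or losses differ between arms, the plotted curves can differ for reasons unrelated to progression. Two programmers could also derive different times from the same data, one following the row and the other following the text above the table.

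**Working it through.** The plan states no event rate, loss rate or power for this endpoint, so there is no figure of its own to reproduce. The counts below are assumptions chosen to show how the rule behaves.

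**1. What each text implies**

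| Participant without support | Row, read literally | Elsewhere in the SAP |
|---|---|---|
| Dies Day 5 | Event-free to Day 28 | No other rule |
| Withdraws or is transferred Day 3 | Event-free to Day 28 | Missing after leaving (8.2 introduction); post-transfer data may be left out (3.6.2) |
| Alive and observed without support at Day 28 | Event-free to Day 28 | Consistent |

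**2. Losses alone.** Assume n = 18 at risk, e = 5 events, and w losses before the first event. Under the literal rule, Day-28 incidence is e/n. If losses are censored when they leave, every event occurs in a risk set drawn from n − w people, so the Kaplan-Meier product reduces to e/(n − w).

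- Literal rule: 5/18 = 27.8%.
- w = 1: 5/17 = 29.4%, a rise of 1.6 points.
- w = 2: 5/16 = 31.25%, shown as 31.3%, a rise of 3.5 points.

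Losses after the last event change nothing, so these are upper values for each w.

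**3. Deaths alone.** Same n and e, with d unsupported deaths and no losses.

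- Cumulative incidence of first support, death competing (Aalen-Johansen): 5/18 = 27.8% for any d, identical to the literal rule.
- Support-free survival, death counted as an event: (18 − 5 − d)/18. For d = 0, 1 and 2 this is 72.2%, 66.7% and 61.1%, so each death costs 1/18 = 5.6 points.

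The literal rule therefore estimates the incidence of first support correctly when nobody is lost. It does not estimate freedom from progression or death, which is how a survival plot of progression is likely to be read.

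**4. Effect on the arm comparison.** For simplicity, assume all 27 control and 54 active participants are at risk and none is lost. Control: 8 supported, 0 unsupported deaths. Active: 12 supported, 4 unsupported deaths.

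| Quantity at Day 28 | Control | Active | Active minus control |
|---|---|---|---|
| Event-free, literal rule | 19/27 = 70.4% | 42/54 = 77.8% | +7.4 points |
| Support-free survival, death as event | 19/27 = 70.4% | 38/54 = 70.4% | 0 |
| Incidence of first support, death competing | 8/27 = 29.6% | 12/54 = 22.2% | −7.4 points |
| Incidence of unsupported death | 0% | 4/54 = 7.4% | +7.4 points |

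The literal curve shows a 7.4-point advantage. The competing-risk display shows the same difference in support, but puts beside it the deaths that offset it.

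**The case against.** The strongest reply is that holding deaths in the risk set to Day 28 is legitimate. With no other early censoring, one minus Kaplan-Meier equals the competing-risk incidence of first support, as step 3 shows. Counting death as an event is a change of estimand and does not correct an error. This stands. What remains is presentation: the SAP does not say that it intends a cumulative incidence, and it asks for a survival plot labelled as progression.

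Second, withdrawals and transfers are not ignored: the introduction to Table 8.1 sets them to missing after they leave. This stands in part. That text gives no censoring date and does not agree with the row. The phrase about Day 28 might also mean the time at which use is judged, in which case the row states no censoring time at all. The mock shells, to which section 8.2 refers for further detail, might settle this, but they are not among the documents.

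Third, deaths are visible elsewhere. Table 8.1 reports 28-day mortality by arm, including groups defined by support around randomization, and the ordinal-scale table carries deaths forward and shows withdrawals. This limits the harm but does not make the curve clear on its own.

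Fourth, the stakes are low. Protocol 4.3 lists the endpoint as exploratory, SAP 3.1 gives no p-values for secondary objectives, and SAP 4.5 says findings need confirmation. This stands.

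**Conclusion.** The row is incomplete and conflicts with two other parts of the SAP. Followed literally, it shows unsupported deaths as 28 days free of progression and keeps people who are no longer observed in the risk set. The importance is minor to moderate.

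The size cannot be known from the documents. Under the assumed 18 at risk and 5 events, one or two early losses move the incidence by 1.6 to 3.5 points, and each unsupported death moves support-free survival by 5.6 points. Two losses in 18 would be 11.1%, above the dropout of less than 10% assumed in SAP 2.4 for the primary endpoint.

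A reader might infer three stronger things that the documents do not support:

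- **That withdrawn or transferred participants are certainly counted as progression-free to Day 28.** The introduction to Table 8.1 points the other way, so only the conflict is established.
- **That the plan understates progression by 6 to 16 points.** Such a figure arises only by redefining the event to include death and adding losses, all on assumed counts: 6/18 = 33.3% is 5.6 points above 27.8%, and 7/16 = 43.8% is 16.0 points above. Deaths alone leave the incidence of first support unchanged.
- **That this is the only time-to-event analysis behind the trial's rationale.** Protocol 3.1 and 5.1 give the rationale as preventing progression to ARDS, and time to ARDS has its own Kaplan-Meier row.

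**What to change.** Replace the single instruction in the row with a rule for each way out:

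1. Withdrawn or transferred without support: censor at the last day with respiratory data. Reconcile this with the introduction to Table 8.1 and with section 3.6.2, including whether post-transfer data from a study hospital count.
2. Known to be alive without support at Day 28: censor at Day 28.
3. Discharged alive: state the assumption made between discharge and the Day-28 call.
4. Death without support: choose one presentation and label it. Either show the cumulative incidence of first support with death as a competing event (Aalen-Johansen), with the incidence of unsupported death beside it, or plot support-free survival with death as an event.

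Censoring at death in an ordinary Kaplan-Meier analysis would not be a repair, because it treats death as uninformative about progression.

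The cost is a few derivation lines and a relabelled figure. Dates of death and daily in-hospital respiratory status are already collected, so no new data are needed. The composite has one downside: it changes what is estimated, from first use of support to first use of support or death. The competing-risk option avoids this.

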- Time since randomization to progression to ARDS
criteria-defined ARDS according to the adapted Berlin criteria as follow:
 - * Within 1 week of a known clinical insult or new or worsening respiratory symptoms
 - * bilateral infiltrates not supposed to be of cardiac origin or fluid overload
 - * $\text{PaO}_2/\text{FiO}_2 < 300$ mmHg
 - * $\text{PEEP} > 5$ cm H₂O on invasive or non-invasive ventilation or flow ≥ 50 L/min on HFOT (Optiflow)
- Time since randomization to progression to ARDS according to D-dimers and complement C5a at randomization
- Incidence of lung function abnormalities at follow up 12-22 weeks post-randomization
- Incidence of lung fibrosis on chest high-resolution computed tomography (HRCT) scan at follow up 12-22 weeks post-randomization

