6.1. Inclusion Criteria

-Recent (≥ 6 days and ≤ 16 days of flu-like symptoms or malaise prior to randomization) infection with COVID-19.

-COVID-19 diagnosis confirmed by antigen detection test and/or PCR and/or positive serology, or any emerging and validated diagnostic laboratory test for COVID-19 within this period. For patients with a negative SARS-CoV-2 PCR and either a positive SARS-CoV-2 antigen or antibody test, the presence of suggestive lesions for COVID-19 on chest-CT scan is mandatory.

-In some patients, it may be impossible to get a confident laboratory confirmation of COVID-19 diagnosis after 24h of hospital admission because viral load is low and/or problems with diagnostic sensitivity. In those cases, in absence of an alternative diagnosis, and with highly suspect bilateral ground glass opacities on recent (< 24 h) chest-CT scan (confirmed by a radiologist and pulmonary physician as probable COVID-19), and a typical clinical and chemical diagnosis with signs of cytokine release syndrome, a patient can be enrolled as probable SARS-CoV-2-infected. In all cases, this needs confirmation by later seroconversion.

-Presence of hypoxia defined as

1) O₂ saturation below 93% on minimal 2l/min O₂ therapy;
and/or

2) PaO₂/FiO₂ below 350 mmHg (Strongly recommended: patient in upright position, after minimal 3 minutes without supplemental oxygen; In ventilated patients PaO₂ can be taken from invasive arterial line and FiO₂ taken directly from mechanical ventilation settings).

-Signs of acute lung injury and/or cytokine release syndrome defined as

ANY of the following

-serum ferritin concentration > 1000 mcg/L and rising since last 24h

-single ferritin above 2000 mcg/L in patients requiring immediate high flow oxygen device (Optiflow) or non-invasive or invasive mechanical ventilation

-lymphopenia defined as < 800 lymphocytes/microliter and two of the following extra criteria

-Ferritin > 700 mcg/L and rising since last 24h

-increased LDH (above 300 IU/L) and rising since last 24h

-D-Dimers > 1000 ng/mL and rising since last 24h

-CRP above 70 mg/L and rising since last 24h and absence of bacterial infection

-if three of the above are present at admission, no need to document 24h rise

-Low dose Chest CT or HRCT or Angio Chest CT scan showing bilateral infiltrates within last 2 days prior to randomization

-Admitted to specialized COVID-19 ward or an ICU ward taking care of COVID-19 patients

-Age ≥ 18 years

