6.2. Exclusion Criteria

- Patients with known history of serious allergic reactions, including anaphylaxis, to Zilucoplan® or inability to receive antibiotic prophylaxis due to allergy to ALL of the antibiotics that can be given for prophylaxis of meningococcal disease
- History of active or past meningococcal disease
- Invasive mechanical ventilation > 24 h at randomization**
- Patient on ECMO at screening
- Clinical frailty scale above 3 before onset of the COVID-19 episode
- Weight below 54 kg as measured max 1 week prior to inclusion
- Weight above 150 kg as measured max 1 week prior to inclusion
- Active bacterial or fungal infection
- Unlikely to survive beyond 48h
- Neutrophil count below 1500 cells/microliter
- Platelets below 50.000/microliter
- Patients enrolled in another investigational drug study
- Patients on high dose systemic steroids (> 8 mg methylprednisolone or equivalent for more than 1 month) or other moderately immunosuppressive drugs (in the opinion of the investigator) for COVID-19 unrelated disorder
- Patients on current complement inhibiting drugs
- Serum transaminase levels >5 times upper limit of normal, unless there are clear signs of cytokine release syndrome defined by LDH >300 IU/L and ferritin >700 ng/ml
- Pregnant or breastfeeding females (all female subjects deemed of childbearing potential by the investigator must have negative pregnancy test at screening)

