3.2.1.3 Nominal Days

The pre-specified protocol nominal days are labelled as follows:

- Day -1
- D1
- D2

- D6
- D15
- D28
- Follow-up

The study protocol specifies that clinical and laboratory parameters be collected as frequently as possible, which would be daily. A window of +/- 1 relative day for each specified nominal day after D2 (+ 1 day for D2) will be allowed if a measurement was not collected on the specified relative day. The window for D28 is +/- 3 days. If a large proportion of data fall outside this window, then increasing the window to +/-2 days for nominal D6, nominal D15 and D28 will be considered.

An additional indicator variable will be derived, DISCHARGE DAY (Y/N), which will identify the relative day that the participants was discharged from hospital. If discharge is on or earlier than relative day 6, between relative day 7 and relative day 15 inclusive or between relative day 16 and relative day 28 inclusive, an additional row mapping the results of the discharge visit to nominal D6, or nominal D15 and nominal D28 respectively. For the primary endpoints a LOCF approach will be utilized for the participants who discharge i.e. if a participant discharges at Day 4 then that oxygenation measure will be mapped to Day 6, Day 15 and Day 28. The approach may be extended to secondary parameters. Data from participants who leave hospital for reasons other than clinical improvement will not be mapped to the nominal days as described above. Participants who die whilst in hospital are not considered as ‘discharged’. Separate indicator variables will be derived to indicate whether a participant has died on a specific relative day and if treatment was discontinued due to an adverse event.

The Nominal Day variable with the above labels will be derived from the relative days and allowable window for all collected endpoints. Since the ideal is to take measurements as frequently as possible, some measurements of some endpoints will not have a Nominal Day associated with them. When these values (without an associated Nominal Day) are to be summarized, graphed or analysed in statistical models, Relative Day will be used as either a continuous variable or categorical as defined in the respective sections. Nominal Day will only ever be used as a categorical variable.

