
Objective 3 Time since randomization to progression to ARDS
	
Randomisation date Date of ARDS diagnosis Derive time variable (days) from date of randomization to date of ARDs diagnosis for each participant. For participants who
	
Kaplan-Meier analysis using PROC LIFETEST. Strata ACTARM. Request Survival plot adjusting axis and heading titles to reflect progression and not response

Endpoint	Derivation	Analysis
	
do not progress to ARDs, time is from date of randomization to date of discharge from hospital or 28 days, whichever is earlier.
 
Derive Censor variable indicating whether Progression to ARDS (censor=0, otherwise censor=1)
	
Output statistics:
 
Appropriate statistics from analysis as indicated in mock shell

Objective 3
 
Duration of ICU stay in participants that enrolled in trial that were on invasive or non-invasive mechanical ventilation or high-flow oxygen devices within 24h prior to or after randomization during 28-day assessment period
 
Duration of ICU stay in participants that enrolled in trial that were on invasive or non-invasive mechanical ventilation for less than 24h prior to or after randomization during 28-day assessment period
	
Use DATES and Vital Signs dataset to calculate variable giving total number of days in ICU for sub-group of patients
	
Summary statistics of variable with Total number of days: n, mean, SD, median, minimum, maximum
 
By treatment arm

Endpoint	Derivation	Analysis

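### The time-to-ARDS analysis keeps participants who may already have ARDS at entry and censors at discharge under Kaplan-Meier, so its curve is not the 28-day probability of progression; the coding of deaths is not stated

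*SAP*

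**What the plan says.** The ARDS row of SAP Table 8.1 (section 8.2) measures days from randomisation to ARDS diagnosis. For participants who "do not progress to ARDs, time is from date of randomization to date of discharge from hospital or 28 days, whichever is earlier". The coding instruction is "Derive Censor variable indicating whether Progression to ARDS (censor=0, otherwise censor=1"), and the method is "Kaplan-Meier analysis using PROC LIFETEST. Strata ACTARM". The row names no at-risk population, no rule for ARDS present at randomisation and no rule for death. SAP section 3.2.1.3, on mapping visits to nominal days, says: "Participants who die whilst in hospital are not considered as" discharged.

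Protocol section 4.3 defines ARDS by four criteria: onset within a week of an insult or of new or worsening respiratory symptoms; bilateral infiltrates not of cardiac or fluid origin; PaO2/FiO2 below 300 mmHg; and PEEP above 5 "cm H₂O on invasive or non-invasive ventilation or flow ≥ 50 L/min on HFOT (Optiflow").

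On entry, Protocol section 6.1 requires "Low dose Chest CT or HRCT or Angio Chest CT scan showing bilateral infiltrates within last 2 days prior to randomization". It accepts PaO2/FiO2 below 350 mmHg, and one of its inclusion criteria names patients who need high-flow oxygen or ventilation. On respiratory support, section 6.2 excludes only ECMO at screening and "Invasive mechanical ventilation > 24 h at randomization".

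**The concern.** A participant who has ARDS at randomisation cannot progress to it. A participant sent home because of improvement does not carry the ARDS risk of those still in hospital, yet Kaplan-Meier with censoring at discharge assumes so. A participant who dies without ARDS has an undefined place in the dataset, and one plausible reading records that person as ARDS-free for the full 28 days.

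Preventing progression to ARDS is the trial's stated justification (Protocol sections 3.1 and 5.1) and a secondary objective in both documents. Progression to ARDS is also left out of adverse event reporting (Protocol 13.5, SAP 10.2), so this row is the main planned comparison of ARDS between arms. A reader will take its curve as the chance of developing ARDS by day 28.

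**Working it through.** The plan states no ARDS, discharge or pre-ARDS death rate and no power for this endpoint, so it has no figure of its own to reproduce here. Every rate below is an assumption.

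**1. Overlap at entry.** The imaging criterion is largely met by the inclusion criteria. For oxygenation, take the documents' admission mean of 320 mmHg and assume a normal distribution with SD 60 to 105. Among values below 350, the share below 300 is Φ((300−320)/SD) / Φ((350−320)/SD), which gives 53% (SD 60) to 69% (SD 105). This covers one criterion only; PEEP or flow must also qualify. Such support is expected in part of the sample: SAP section 6.2, in its ferritin item, describes ordinal scores 2 or 3 (ventilated or high flow) as the expected population. So some participants can have ARDS at entry; how many is unknown.

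**2. Coding of entry ARDS.** Assume 30% have ARDS at entry, and incidence among the rest is 22.5% v 40% (ratio 0.56).
- Coded as events: (0.3 + 0.7×0.225) / (0.3 + 0.7×0.40) = 0.4575/0.58 = 0.79.
- Not coded as events: (0.7×0.225) / (0.7×0.40) = 0.56.

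The SAP does not say which applies.

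**3. Discharge.** Assume constant daily hazards of 0.04 (ARDS) and 0.09 (discharge), no deaths, and no ARDS after discharge. With the ARDS hazard acting for T days, incidence = 0.04/0.13 × (1 − exp(−0.13T)) and one minus Kaplan-Meier = 1 − exp(−0.04T).
- T = 28: 0.308 × (1 − exp(−3.64)) = 30%, against 1 − exp(−1.12) = 67%.
- T = 7: 0.308 × (1 − exp(−0.91)) = 18%, against 1 − exp(−0.28) = 24%.

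**4. Between-arm comparison and death.** Use daily steps over 28 days with an ARDS hazard of 3% per day in both arms. Each day, the fraction still in hospital and ARDS-free loses ARDS, discharge and death cases in proportion to their hazards. Under the literal rule, ARDS-free deaths stay in the Kaplan-Meier risk set to day 28; under the alternative they leave it at death. Figures are A v B.

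| Assumption | Cumulative incidence of ARDS | 1 − KM, deaths held to day 28 | 1 − KM, deaths censored at death | ARDS or death |
|---|---|---|---|---|
| Discharge 12% v 8% per day; death 0.5% in both | 19.2% v 25.2% | 45.5% v 49.5% | 57.4% v 57.4% | 22.4% v 29.4% |
| Death 2% v 0.5% per day; discharge 8% in both | 22.6% v 25.2% | 37.4% v 49.5% | 57.4% v 57.4% | 37.7% v 29.4% |

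In the first scenario a 6-point difference in incidence shows as 4 points or none. In the second, the arm with more deaths looks 12 points better on ARDS under the literal rule, while ARDS-or-death is about 8 points worse.

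**5. Neighbouring rows.** The Table 8.1 row for time to first high-flow or ventilatory support excludes participants ventilated within 24 hours of randomisation and censors non-users at day 28, not at discharge. The row for time to sustained improvement states where deaths are placed. The ARDS row does none of this and gives no reason.

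**The case against.** The strongest reply is about weight. Protocol version 6.0 places time to ARDS among the exploratory endpoints, and SAP section 3.1 gives no p-values for endpoints under secondary objectives. The neighbouring support endpoint covers much of the same progression, because ARDS by this definition requires high flow or ventilation. All of that stands and limits the consequence, but an interval around the wrong quantity is still wrong.

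The rates in the working are invented, and the gap shrinks to 6 points if ARDS risk is confined to the first week. That stands too: the defect is certain in kind, not in size. It can also be said that censoring at discharge still permits a comparison of ARDS hazards among those in hospital. That is fair, but the planned curve will be read as a probability of progression.

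On death, a reader might infer that the SAP scores early death as success. The documents do not establish this. The result comes from joining the ARDS row to a sentence written for visit mapping. SAP Table 8.1 computes hospital stay from a discharge date for everyone and separately for survivors, so a death date may be stored as the end of stay. Deaths would then be censored at death, which is informative but different.

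The mock table shells, to which the SAP refers for further detail, are not in the public documents and may settle some of this.

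**Conclusion.** The concern holds as a defect of estimand and derivation. Following the SAP as written gives a one-minus-Kaplan-Meier curve that is not the 28-day probability of progressing to ARDS. It is too high whenever discharged patients have a lower later risk than those still in hospital, and it includes participants who may have ARDS at the start. The illustrations run from 18% v 24% to 30% v 67%, depending on how long the ARDS hazard lasts.

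Stronger readings go too far. The documents do not show that the treatment comparison will be wrong in a known direction, because they give no ARDS, discharge or pre-ARDS death rates by arm. Nor do they show that entry ARDS dilutes the effect: the ratio moves from 0.56 to 0.79 only if those cases are coded as events. The primary analysis and sample size are unaffected. The change is still worth making, because progression to ARDS remains a secondary objective and the repair is cheap.

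**What to change.** Amend the ARDS row of SAP Table 8.1 before database lock:

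- Restrict the analysis to participants who do not meet the Protocol 4.3 definition at randomisation, and state how ARDS dated on or before randomisation is identified and coded. Blood gas, CT, ventilation method and flow are planned for collection; PEEP is listed for ICU patients, so say what applies where it is missing.
- Replace one minus Kaplan-Meier with cumulative incidence (Aalen-Johansen) by arm with 95% confidence limits, treating death without ARDS as a competing event.
- Treat live discharge as a competing event, or carry those participants as ARDS-free to day 28 as a stated assumption. The day 28 call cannot verify it: it collects no blood gas, imaging or ventilator data, and progression to ARDS is not reported as an adverse event.
- Add ARDS-or-death by day 28. Cumulative incidence alone still counts an ARDS-free death as no ARDS, so only the composite stops early death from appearing as a good outcome.

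The cost is a smaller at-risk set, with wider intervals in a trial of 81, and a little more programming. No new visits or measurements are required.
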